Northwestern University Feinberg School of Medicine
Department of Anesthesiology
Protocol

Title: Incidence of Post-Dural Puncture Headache following Unintentional Dural Puncture: A Randomized Trial of Intrathecal Morphine versus Saline

Principal Investigator: [name]. **Co-investigator (s):** [name]

Affiliation: Department of Anesthesiology
Northwestern University Feinberg School of Medicine

Institution: Northwestern Memorial Hospital

Research Aims:

- 1. Research Questions(s):** Does the administration of intrathecal morphine after delivery reduce the risk of post-dural puncture headache (PDPH) following unintentional dural puncture (UDP) with a 17-g Tuohy needle in obstetric patients?
- 2. Hypotheses:** Intrathecal morphine decreases the incidence of PDPH as compared to placebo after UDP with a Tuohy needle in obstetric patients.

Background: Unintentional dural puncture is a known risk of neuraxial techniques, occurring in roughly 1% of all epidural catheter placements.¹⁻³ The incidence of PDPH after unintentional dural puncture is 50-80%.³⁻⁵ The International Headache Society has defined PDPH as a headache that occurs following a dural puncture, worsens within 15 minutes after sitting or standing and improves within 15 minutes after lying, with at least one of the following: neck stiffness, tinnitus, hypacusia, photophobia, or nausea. The headache develops within 5 days after dural puncture and resolves either spontaneously within 1 week or within 48 hours after effective treatment of the spinal fluid leak (usually by epidural blood patch).⁶ PDPH can be a significant cause of maternal morbidity in the obstetric patient. In addition to interfering with the mother's ability to care for her newborn, treatment of PDPH can increase health care costs by prolonging the length of hospitalization and number of emergency room visits.⁷

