On postpartum days 1-5, all patients will be visited daily while inpatient and called by phone after discharge from the hospital. The following information will be also recorded in this study: presence or absence of PDPH (as defined by the International Headache Society), signs and symptoms of cranial nerve injury, the patient's verbal rating score for pain (VRSP, 0-10 scale), current headache treatments including oral analgesics, intravenous caffeine, or epidural blood patch, side effects of intrathecal morphine (respiratory depression, nausea, vomiting, pruritus, urinary retention. Patients who develop a headache will be followed for 3 days after the resolution of their headache. Physician observers will make treatment recommendations according to the following protocol (previously described by Scavone et al, 2004¹⁵): Mild postural headaches (defined as VRSP <4) will be treated with conservative therapy including oral hydration, increased oral caffeine intake, and oral analgesics as needed. Moderate postural headaches (defined as VRSP 4-6 without limitation of childcare ability) will also receive conservative therapy. Patients with moderate postural headaches limiting childcare abilities, and patients complaining of severe postural headaches (defined as VRSP >6) will be advised to undergo a therapeutic epidural blood patch (EBP). This treatment will consist of the epidural injection of 20 mL of autologous blood over 2 to 3 min through the epidural needle, injected at the level of the presumed UDP or one level below. The patient will be positioned in the sitting position for the procedure and then repositioned supine for a period of 1 hour after the epidural blood injection. The EBP will not be performed for at least 24 hours after dural puncture. If the EBP fails to relieve the headache after 24 hours, or if the headache recurs after successful treatment, the EBP may be repeated. The protocol outlined above follows standard procedure at NMH.

4. Risks/Benefits:

Risks to study patients include: itching, nausea, vomiting, urinary retention, constipation, dizziness, hypotension, depression of cough reflex and slowing of respirations. The rare risk is respiratory depression leading to respiratory arrest.

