The presumed risks are similar to that assumed by any parturient who receives spinal morphine for Cesarean delivery, which is common practice. To minimize the risk of apnea, patient will be monitored postpartum in the same manner that patients receiving neuraxial morphine for Cesarean delivery are routinely monitored as described above.

If any patient experiences nausea, vomiting or pruritus, she will be treated with medications based on the clinical scenario as evaluated by the attending anesthesiologist on duty who will not be blinded to treatment group. There is also a risk of loss of confidentiality.

Confidentiality: Access to electronic data is computer password protected. All data will be deleted from the password protected computer 5 years after manuscript preparation. Electronic and paper documents will be destroyed using current technology. The paper documents will be shredded using the current vendor for HIPAA sensitive documents using the current technique.

Data Analysis:

1. **Data collection form:** Data collection form attached.

2. **Data evaluation:** The primary outcome is the incidence of PDPH. The intrathecal morphine and saline groups will be compared using the Fisher's exact test. The clinical characteristics of the study groups will be compared between groups using the Mann Whitney test for interval and continuous data and a χ^2 statistic for nominal data. Secondary outcomes include severity of headache, need for epidural blood patch, rate of neuraxial infection, neuraxial complications. $P < 0.05$ will be required to reject the null hypothesis.

3. Interpretation of Anticipated Results: A reduced incidence of PDPH in the intrathecal morphine group without an unacceptable incidence of side effects would support the effectiveness of its administration after UDP.

Budget:

- 1. Materials:** Preservative free morphine (2-mL) 1000 microgram ampule – cost 80 cents per vial for 64 patients. Preservative free 0.9% saline (10-mL) vial – cost 35 cents per vial for 64 patients. The total cost for study drugs is \$74.75, which will be provided by the Department of Anesthesiology.
- 2. Labor Requirements:** Obstetric anesthesiology research nurses and obstetric anesthesiology fellows will recruit patients for the study and will perform all data collection.
- 3. Presentation Cost:** This project will be presented at a national meeting such as ASA or SOAP.

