Consent: *(Provide a consent form in the relevant IRB format. The template for these forms can be found on the Web at: <http://www.research.northwestern.edu/opr5/irb/templates/>)*

Additional information for preparation of an IRB Submission:

NA

Incidence of post-dural puncture headache following unintentional dural puncture: a randomized trial of intrathecal morphine vs. saline

DATA COLLECTION FORM

Study Number: _____

Date: _____

EGA: _____

Parity: _____

Height (inches): _____

Weight (kilogram): _____

Procedure performed by: _____

If resident/fellow specify level of training PGY- _____

Loss of Resistance - air / saline

Dural puncture interspace - _____

Intrathecal Catheter Placement: Date _____ Time _____ Location (skin) ____ cm

Intrathecal Catheter Removal: Date _____ Time _____ Location (skin) ____ cm

Total infusion dose: _____ mLs

Mode of delivery - Vaginal / Forceps or Vacuum Assisted

Start of pushing - _____ End of pushing - _____

Delivery time - _____ Time of removal of catheter _____

Aspirate of CSF prior to drug administration - yes / no

Incidence of post-dural puncture headache following unintentional dural puncture: a randomized trial of intrathecal morphine vs. saline

Patient Study Number _____

Postpartum day # _____

Evaluator: _____

Date: _____ Time: _____ Presence of PDPH yes / no
If yes, Headache VPRS score (1-10): 0 1 2 3 4 5 6 7 8 9 10

Current Headache therapy (please circle and specify doses when appropriate)

1. Hydration _____
2. Oral analgesics _____
3. IV analgesics _____
4. IV Caffeine _____
5. Epidural blood patch date - _____
(please fill out EBP data sheet with details)

Headache VPRS score after treatment _____

Cranial nerve involvement - yes / no

If yes, please specify _____

Presence of backache - yes / no

Backache VPRS score 0 1 2 3 4 5 6 7 8 9 10

Signs/symptoms of infection

1. Max Fever in last 24hours _____
2. Superficial (i.e., swelling, redness, purulence around site) yes / no What? _____
3. CNS (i.e., meningitis, epidural abscess) _____

Lower extremity peripheral nerve symptoms

1. Weakness (where) _____
2. Paresthesia (where) _____

Recommended Therapy (please circle all that apply)

1. Hydration
2. Oral analgesics
3. IV analgesics
4. IV Caffeine
5. Epidural blood patch

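### The daily form asks for a headache score only when PDPH is 'yes', although the Methods ask for a pain score from every patient, and headache severity has no stated analysis set

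*Combined protocol and SAP*

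**What the plan says.** **Methods, 3. Protocol specific methods.** Follow-up covers everyone: "On postpartum days 1-5, all patients will be visited daily while inpatient and called by phone after discharge from the hospital". The items to be recorded include the patient's "verbal rating score for pain (VRSP, 0-10 scale"), with no condition on PDPH. Treatment advice is graded by that score for postural headaches, beginning with "Mild postural headaches (defined as VRSP <4"). Extended follow-up is triggered by any headache: "Patients who develop a headache will be followed for 3 days after the resolution of their headache".

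**Background.** The IHS definition, which the Methods adopt for the recorded outcome, needs more than a postural pattern. The headache must come "with at least one of the following: neck stiffness, tinnitus, hypacusia, photophobia, or nausea".

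**Data collection form, daily page.** The evaluator circles yes or no for PDPH, and the next item is "If yes, Headache VPRS score (1-10"), followed by a printed scale that runs from 0 to 10. There is no item for a headache that is not PDPH. The current-therapy list and a score after treatment carry no visible condition. Lower on the page, after a yes/no item for backache, stands "Backache VPRS score 0 1 2 3 4 5 6 7 8 9 10", without the words 'If yes'.

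**Data Analysis, 2. Data evaluation.** "Secondary outcomes include severity of headache", but no analysis set, day, summary or test is given for it. The Mann-Whitney sentence there covers the clinical characteristics of the groups.

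**The concern.** The Methods and the form disagree on who is scored. The Methods describe a score for all patients. The form, taken literally, skips any patient whose headache is not classified as PDPH, including one with a postural headache but none of the accompanying features. A score not taken on the day cannot be recovered later.

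This matters because severity of headache has no analysis rule. Once the scores sit mainly in PDPH patients, two analyses come to hand, and each has a weakness:

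- **Compare severity among PDPH patients only.** The treatment is meant to change who enters that subset, so randomisation no longer protects the comparison. If morphine prevents mainly mild headaches, those left in the morphine arm are more severe on average and morphine looks harmful, although it has made no headache worse. If it prevents mainly severe ones, the bias is reversed.
- **Set everyone without PDPH to 0.** This keeps the randomised groups but codes any headache outside the IHS definition as no pain.

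**Working it through.** **1. The plan's own figure.** Methods, 1 gives 64 per group, risks of 0.50 and 0.25, and a two-sided Fisher's exact test at 0.05. Exact enumeration over the two binomials gives power 0.802 and an actual significance level of 0.0298. The stated 80% and 0.03 are reproduced and are not in dispute.

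**2. Size of a PDPH-only set at those rates.**
- Saline: 64 × 0.50 = 32 (95% binomial range 24 to 40).
- Morphine: 64 × 0.25 = 16 (95% binomial range 9 to 23).

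**3. What such a comparison could detect.** By normal approximation, the standardised difference detectable with 80% power at two-sided 0.05 is (1.96 + 0.84) × √(1/n₁ + 1/n₂).
- 32 vs 16: 2.80 × √(1/32 + 1/16) = 0.86 SD. Simulating the Mann-Whitney test with normal scores gives 80% power at about 0.9 SD.
- 64 vs 64, if every patient had a score: 2.80 × √(2/64) = 0.50 SD.

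**4. Bias of a PDPH-only Mann-Whitney test.** The documents give no score distribution and no prevention pattern, so both are assumed. Trials of 64 per arm were simulated with 50% headache risk. In the morphine arm each headache was prevented with a probability depending on its score, rescaled to 50% overall, so PDPH is always 50% vs 25%. Morphine worsens no headache. Four score distributions on 1-10 were used (uniform, bell-shaped around 5.5, skewed low, peak at 8), with 4,000 trials per cell and Monte Carlo error of at most 0.8 points. A two-sided 0.05 test should err 2.5% each way.

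| Assumed prevention pattern | Significant result among PDPH patients |
|---|---|
| Unrelated to severity | 2-3% each way |
| 3:2 greater for scores 1-5 than for 6-10 | morphine 'worse' in 4-8% |
| Falls evenly 3:1 from score 1 to score 10 | morphine 'worse' in 9-16% |
| Mildest prevented first (extreme) | morphine 'worse' in 83-86% |
| Severest prevented first (extreme) | morphine 'better' in 82-86% |

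No moderate pattern favouring prevention of severe headaches was simulated. For a score distribution symmetric about 5.5, such as the uniform, reversing the scale (score s becomes 11 − s) turns each moderate pattern into its opposite and 'worse' into 'better'. The error rates then carry over in the other direction. For the two skewed shapes only the direction can be inferred.

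**5. Headaches that would go unscored.** Expected patients without PDPH: 64 × 0.50 + 64 × 0.75 = 80 of 128. The documents give no rate of non-IHS headache. If a fraction f of these 80 had one, 80f would be unscored: 8, 16 or 24 for f = 10%, 20% or 30%. These fractions are assumptions.

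**6. Does zero-filling them bias the comparison?** With no treatment effect, 50% headache in both arms, uniform scores and 10, 20 or 30% of headaches set to 0 equally in both arms (3,000 trials each), the test was significant in 2-3% each way, so there was no bias. Unequal loss and loss of power were not examined.

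**The case against.** - **The Methods already ask for the score in everyone.** This stands. A reader might infer that the trial plans not to collect severity outside PDPH, but the documents show a conflict between text and form. Clinicians also need a score to grade postural headaches, so some may be noted elsewhere. The blood patch data sheet that the form mentions is not in the documents and would cover only patched patients. None of this puts the pre-treatment score on the daily page.
- **No PDPH-only test is planned.** This also stands. The error rates in the table belong to an analysis that the form invites, not to one that the plan names.
- **The 82-86% figures.** A reader might take these as the likely bias. They come from near-deterministic prevention, for which the documents give no support. They show the limits and the two directions, and the argument does not rest on them.
- **Unscored headaches bias the result.** A reader might infer this too. Their rate is assumed and equal loss shows no bias, so what is shown is a loss of meaning and of data.
- **Backache as a precedent.** The backache score lacks the words 'If yes' but also follows a yes/no item. It does not prove that every patient was meant to be scored.
- **The all-patient comparison mostly repeats the primary result.** Largely true; the cost is given with the fix.

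The missing analysis set and the mismatched scale label would be minor if taken alone. They matter here because the form also limits which data will exist.

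**Conclusion.** The concern holds as a conflict between the Methods and the daily form. Followed as printed, the form gives a headache outside the IHS definition no pre-treatment score. A secondary outcome without a stated set, summary or test is then captured mainly in about 32 saline and 16 morphine patients, a subset defined by the primary outcome.

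The size is modest. A PDPH-only test, if used, is unbiased when prevention is unrelated to severity. It calls morphine falsely worse in about 4-16% of trials under the two moderate patterns, and can err the other way if severe headaches are preferentially prevented. These figures rest on the planned rates and on assumed score distributions and prevention patterns.

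The finding affects one secondary outcome only. It should be corrected because the data cannot be recovered later and the correction costs little.

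**What to change.** **Form.** Reconcile the daily page with the Methods. Take the headache score out of the 'If yes' branch, so that a 0-10 score (0 = no headache) is recorded for every patient at each day 1-5 contact. Align the 1-10 label with the printed 0-10.

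**Data evaluation.** Compare the worst score over days 1-5 between the randomised groups by Mann-Whitney. The window should be common to all patients because those with a headache are followed for longer, and a worst-ever score would give them more chances of a high value. Add two analysis rules:
- for missing scores, since 170 are to be randomised and the calculation needs 128, so up to 170 − 128 = 42 are allowed for exclusions and losses;
- for scores taken after a blood patch. This is a rule for the analysis only and changes no treatment.

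Report scores from later headache follow-up descriptively, since a late headache may peak after day 5, and do the same for severity among PDPH patients.

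**Cost.** One item moved, one label corrected and a few sentences added. The daily visits and calls already take place.

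**Downside to state.** The all-patient score measures overall headache burden and overlaps with the primary outcome. In the simulations, with no other headaches assumed, it is significant in 81% of trials and agrees with Fisher's test in 93-94% if prevention is unrelated to severity. Under the two moderate patterns the figures are 73-80% and 91-94%. It should be read as supporting the primary result, not as independent evidence.
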